#### **5.2.6. Migration**

Assessment of significant migration of the implant or complete expulsion (significant is defined  $> 5$  mm) will be assessed from X-ray images (point of reference is the tip of the U-portion implant identified on the corresponding X-ray image). Baseline images will be made before discharge of the patient. Further images will be made after 3 months and after 24 months, and annually thereafter. All X-ray images from all centers will be evaluated centrally by an experienced radiologist.

#### **5.2.7. Spinous Process Fracture**

Spinous process fractures will be assessed from X-ray at all time points and CT at 24 months. Subjects with confirmed, symptomatic spinous process fractures will also have CT taken at 60 months. All X-rays and CTs from all centers will be evaluated centrally by an experienced, independent radiologist. Presence of spinous process fractures will not be considered a treatment failure.

### **6. Study Criteria for Safety**

The safety assessments will include documentation of Adverse Events and SAEs and device/procedure related adverse events (e.g. breaking of implants). Specific AEs will be summarized according to incidence (per patient) and counts of AE over time. Further, the following criteria will be documented:

- Assessment of revisions and additional stabilizations.
- Assessment of epidurals.
- Assessment of narcotics usage.

### 6.1. Adverse Events:

At each visit all adverse events, whether voluntarily reported by the patient or observed by the investigators, will be recorded in the appropriate eCRF. Data collected will include:

- Description of sign or symptom,
- Date of start and date of end of the adverse event,
- Event severity (mild, moderate, severe),
- Frequency (once/intermitting/continuous),
- Relation to treatment (definite, probable, possible, unlikely, not related),
- Event treatment (e.g., none, non-drug therapy, medications, injection)

An AE is any undesirable clinical occurrence in a subject whether or not it is related to the device/procedure. Any condition at baseline that is recorded as a preexisting condition is not an AE unless it worsens in intensity or duration. The collection of AEs will begin in the operating room when the incision(s) is made that starts the treatment procedure. All AEs that occur through completion of the final follow-up visit, whether observed by the investigator or by the subject, and whether or not thought to be device/procedure related, will be reported in detail on the appropriate eCRF and followed to resolution.

The description of the AE will include the date and time of onset, severity, causal relationship to the device or procedure, any treatment required, and the outcome of the event. In addition to the AE categories listed below, AEs will be listed as "Early," within 30 days of surgery, or "Late," more than 30 days after surgery. The investigator will follow each subject who experiences an AE until the event resolves. In the unusual circumstance that an AE has not resolved by the time of the subject's completion of the study, an explanation will be entered on the appropriate eCRF.

Anticipated adverse events, as described in the coflex IFU, are:

Adverse events that are associated with any surgery include:

- Infection (deep or shallow)
- Pneumonia (lung infection)
- Atelectasis (collapsed lung)
- Septicemia (blood poisoning)
- Injury to blood vessels
- Soft tissue damage
- Phlebitis (inflammation of the blood vessel in your leg)
- Thromboembolus (blood clot in legs) or pulmonary embolism (blood clot in lung)
- Hemorrhage (excessive bleeding)
- Respiratory distress (difficulty breathing)
- Pulmonary edema (abnormal collection of fluid in lungs)
- Reactions to the drugs or anesthetic agent used during and after surgery
- Reactions to transfused blood

- Failure of the tissue to heal properly (e.g., hematoma [a pocket of blood cause by bleeding from a broken blood vessel]; seroma [buildup of clear body fluid in the tissue]; dehiscence [failure of the incision to completely heal which may allow it to reopen], etc.) which may require drainage, aspiration (removing a substance using suction); debridement (surgery to clean foreign material and dead tissue out of a wound); or other intervention
- Incisional pain
- Heart attack
- Stroke
- Death

Adverse events that are associated with decompression:

- Damage to nerves leading to sensory or motor deficits (changes in the sensation and/or muscle weakness in your legs)
- Paralysis (loss of ability to move muscles with the loss of feeling also)
- Paresthesias (a sensation of pricking, tingling, or creeping on the skin)
- Cauda equina syndrome (severe nerve compression cutting off sensation and movement to your legs with possible loss of bowel and bladder function)Damage to nerves, blood vessels, and nearby tissues including, for example, muscle and/or ligament injury
- Epidural bleeding (bleeding around the membrane covering the tissue surrounding your spinal cord that may require a blood transfusion or another operation)
- Epidural hematoma (a pocket of blood caused by a broken blood vessel or bone bleeding in the membrane covering the nerves or the tissues surrounding your spinal cord)
- Epidural fibrosis (scar tissue formation on the membrane covering the nerves)
- Instability of the operated or adjacent vertebrae
- Blindness by prolonged pressure on the eye during the operation
- Osteolysis
- Injury to the spinal cord or the nerves leaving or entering the spinal cord
- Loss of the ability to control bowel or bladder function)
- Retrograde (reverse) ejaculation, sexual dysfunction, or possible sterility
- Disc herniation ("slipped disc")
- Injury to blood vessels
- Dural violation, with or without reaction (injury of the membrane [dura] surrounding the spinal nerves which may or may not result in leakage of spinal fluid)
- Impaired muscle or nerve function
- Hemorrhage (excessive bleeding)
- Epidural injection reaction
- Epidural injection failure
- Fracture of the vertebrae, spinous process (the part of your spine that you can feel through the skin on your back), or other damage to bony structures during or after surgery
- Postoperative muscle and tissue pain
- The chance that the surgery will not reduce the pain or symptoms felt before the surgery
- Spontaneous fusion (unplanned, self-generated fusion of the vertebra)
- The spine may undergo unfavorable changes or deterioration at the operated level(s) and/or the levels above and below including loss of proper spinal curvature, correction, height, and/or reduction, or malalignment, which may require another surgery

Adverse events that are associated with coflex implant:

- Implant malposition or orientation (the implant could be improperly positioned)
- Allergies to implant materials (possible allergic reaction to the metal)

- Possible wear debris (there may be some wearing of the implant material against bone or another part of the implant that creates very small particles; it is possible that these particles may eventually cause the local tissues such as bone, nerves and nearby soft tissue to respond badly)
- Impantation of the study device at the wrong level of the spine
- Fracture of the vertebrae, spinous process, or other damage to bony structures during or after surgery
- Implant may loosen, deform (permanently change shape), break, fatigue (wear out), or move which may require another surgery to correct the problem and/or remove the implant
- Instruments also may break or malfunction in use, which may cause damage to the operative site or adjacent structures

## 6.2. Assessment of Severity:

- Mild: Awareness of signs or symptoms, but easily tolerated and are of minor irritant type causing no loss of time from normal activities. Symptoms do not require therapy or a medical evaluation; signs and symptoms are transient.
- Moderate: Events introduce a low level of inconvenience or concern to the participant and may interfere with daily activities, but are usually improved by simple therapeutic measures; moderate experiences may cause some interference with functioning.
- Severe: Events interrupt the participant's normal daily activities and generally require systemic drug therapy or other treatment; they are usually incapacitating.

## 6.3. Relationship to Device / Procedure

The investigator will evaluate the relationship of the adverse event to the research intervention according to the following definitions. The term "device-related," as it pertains to adverse events, means that the event was or may have been attributable to a device, or that a device was or may have been a factor in an event, including those occurring as a result of malfunction, poor manufacture, inadequate labeling, or improper design.

The term "procedure-related," as it pertains to adverse events, means that the event was or may have been attributable to a procedure, or that a procedure was or may have been a factor in an event.

- **Definite**  
The adverse event is clearly related to the investigational agent(s) or research intervention: the adverse event has a temporal relationship to the administration of the investigational agent(s) or research intervention, follows a known pattern of response, or is otherwise logically related to the investigational product, and no alternative cause is present.
- **Probable**  
The adverse event is likely related to the investigational agent(s) or intervention: the adverse event has a temporal relationship to the administration of the investigational agent(s) or research intervention, follows a known or suspected pattern of response, or is otherwise logically related to the investigational product, but an alternative cause may be present.
- **Possible**  
The adverse event may be related to the investigational agent(s) or intervention: the adverse event has a temporal relationship to the administration of the investigational

agent(s) or research intervention, follows a suspected pattern of response, or is otherwise logically related to the investigational product, but an alternative cause is present.

- **Unlikely**

The adverse event is doubtfully related to the investigational agent(s) or intervention: the adverse event has a temporal or other relationship to the administration of the investigational agent(s) or research intervention, but follows no known or suspected pattern of response, and an alternative cause is present.

- **Not Related**

The adverse event is clearly NOT related to the investigational agent(s) or intervention: the adverse event has no temporal or other relationship to the administration of the investigational agent(s) or research intervention, follows no known or suspected pattern of response, and an alternative cause is present.

#### 6.4. Serious Adverse Events

A serious adverse event (SAE) is any adverse event that:

- Results in death;
- Is life-threatening; the subject was at substantial risk of dying at the time of the adverse event, or use or continued use of the device or other medical product might have resulted in the death of the patient;
- Results in hospitalization (initial or prolonged);
- Results in disability or permanent damage; the event resulted in a substantial disruption of the person's ability to conduct normal life functions;
- Results in a congenital anomaly or birth defect;
- Requires intervention to prevent permanent impairment or damage; medical or surgical intervention was necessary to preclude permanent impairment of a body function, or prevent permanent damage to a body structure.
- Results in any other serious, important medical events; the event does not fit the other outcomes, but the event may jeopardize the patient and may require medical or surgical intervention to prevent one of the other outcomes.

In case of Serious Adverse Events (SAE), the Investigator must notify the CRO as soon as possible but at least within **one working day** after becoming known to the Investigator, by entering the data in the Electronic Data Capture (EDC) system.

The first report of a SAE must be completed within one working day after becoming known to the Investigator by completing in full the Adverse Event eCRF, i.e., subject's initials, date of evaluation, subject's ID, surgeon's name, visit type, onset date, severity of event, relationship to device, relationship to procedure and event classification. The report of a SAE by EDC will alert the clinical trial manager at MCRA via e-mail once the eCRF has been submitted via Electronic Data Capture (EDC).

If for some reason, the EDC system is not accessible, the SAE notification may be submitted via email to [[contact]](mailto:[contact]). The email should include the Investigator's name, subject's ID, and a description of the event. This notification method should only be used if the EDC data entry cannot be completed within the specified time requirement (i.e., 1 working day). As soon as the EDC system is available, the Adverse Event eCRF should be completed.

New SAEs will only be documented for each patient until the last study related patient visit.

MDRs have to be reported within 30 working days. In case of acute risk the incident has to be reported immediately.

#### **6.4.1. Serious Device-Related Adverse Events**

In the coflex cohort: presence of a major device-related adverse event is defined as an event simultaneously having a severity rating of 'Serious' and a device relatedness of 'Definitely'. In the control cohort, since there is no device, this endpoint will be identified as any serious AE that is classified as definitely related to surgery.

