	the PAS population relative to device performance defined by IDE study results.
CRITERIA for EVALUATION: 1. EFFECTIVENESS	
Objective 1: Month 60 Composite Clinical Success (CCS)
 
A similar CCS endpoint as was used in the IDE will be used to compare clinical status of patients implanted with the coflex® device relative to surgical decompression at 60 months.
 
Month 60 success for this comparison will require the following items:
 
 
❖ At least a 15 point improvement relative to pretreatment baseline in the Oswestry Disability Index (ODI, range 0-100).
 
❖ No reoperations, revisions, removals, or supplemental fixation at the index level(s);
 
❖ No <math>\geq 2</math> injections or series of injections for any lumbar level**, or nerve block procedures performed to treat spinal stenosis at any lumbar level(s); or a single injection within 12 months of the 5 year endpoint.
 
 
**A series of injections is considered 2-3 injections performed between 24-hour and one week intervals designed to treat a single pain event. Secondary injections performed due to patient demand or recurrence of symptoms following the initial injection are considered separate injections and would constitute a study failure.
 
Additional details, justification, and sensitivity analyses are described in the main protocol text below.
 
Objectives 2 and 3: Month 24 CCS
 
For the comparison to decompression, the Month 24 CCS will be slightly modified to include any surgical intervention at index level(s). This is because the decompression only group receives no device. In summary, when comparing coflex® in conjunction with decompression to decompression alone, Month 24 CCS will require:
 
 
• No “Treatment Failure” on or before the exact 2-year anniversary of the index surgery. Treatment Failure will include: 
 
1. No surgical intervention at the index level
 
2. No lumbar epidural steroid injection including nerve root blocks and facet blocks at any lumbar level
 
 
 
• At least a 15-point improvement relative to pretreatment baseline in the Oswestry Disability Index (ODI, range 0-100).
 
• No major device-related adverse event defined as an event simultaneously both 'Serious' and 'Definitely' on or
 

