	
before the exact surgical two-year anniversary. In the decompression alone group, since there is no device, this endpoint will be identified as any serious AE that is classified as definitely related to surgery.
 
Note: The IDE study defined this CCS component as severe and definitely-related. This has been changed to serious and definite for consistency with other spine studies for Objectives 2 and 3 only.
 
Objective 4: Month 24 CCS
 
The identical Month 24 CCS endpoint defined for the IDE study will be used to compare PAS results to IDE study results. These results will be used to update the Bayesian posterior probabilities of non-inferiority and superiority relative to fusion that are summarized in the coflex® SSED.
 
Secondary Criteria:
 
 
• ODI change compared to baseline at 24 and 60 months as a continuous variables and in terms of achieving at least a 15 point improvement.
 
• Change in Visual Analog Scale (VAS) for low back pain (on the 100 mm scale) after 24 and 60 months compared to baseline as a continuous variables and in terms of achieving a 20 point improvement.
 
• Change in leg pain using a Visual Analog Scale (VAS) 100 mm scale after 24 and 60 months compared to baseline as a continuous variable and in terms of achieving a 20 point improvement.
 
• Change in worst leg pain using Visual Analog Scale (VAS) 100 mm scale after 24 and 60 months compared to baseline as a continuous variable and in terms of achieving a 20 point improvement
 
• Change of Zurich Claudication Questionnaire (ZCQ) after 24 and 60 months compared to baseline:               
 
1. Symptom severity (range 1-5)
 
2. Physical function (range 1-4)
 
3. Patient satisfaction (range 1-4, no baseline)
 
4. ZCQ Overall Success (<math>\geq 2</math> of 3 of the following)                   
 
1) Improvement in symptom severity <math>\geq 0.5</math>
 
2) Improvement in physical function <math>\geq 0.5</math>
 
3) Satisfied or somewhat satisfied as defined by a score of <math>\leq 2.5</math> points on the patient satisfaction domain.
 
 
 
5. ZCQ Overall Success components
 
 
 
• Maintenance or improvement in EQ-5D compared to baseline
 

--	---

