##### **Objective 2:**

The second objective of this study is to compare clinical status of patients implanted with the coflex® device in conjunction with surgical decompression relative to surgical decompression alone at two years post operatively by confirming clinical non-inferiority in terms of Month 24 composite clinical success (CCS) defined similarly to the IDE study endpoint. This objective will be achieved by conducting a Bayesian test of the null hypothesis that the probability of achieving

Month 24 CCS among patients implanted with the coflex® device in conjunction with surgical decompression is no more than 10% smaller than that for patients undergoing surgical decompression alone. An informative prior distribution for the coflex® group was formulated on the basis of results contained in the coflex® SSED.

For the comparison to decompression, the Month 24 CCS will be slightly modified to include any surgical intervention at index level(s). This is because the decompression only group receives no device. In summary, when comparing coflex® in conjunction with decompression to decompression alone, Month 24 CCS will require:

- No “Treatment Failure” on or before the exact 2-year anniversary of the index surgery. Treatment Failure will include:
  1. No surgical intervention at the index level
  2. No lumbar epidural steroid injection including nerve root blocks and facet blocks at any lumbar level
- At least a 15 point improvement relative to pretreatment baseline in the Oswestry Disability Index (ODI, range 0-100).
- No major device-related adverse event defined as an event simultaneously both ‘Serious’ and ‘Definitely’ on or before the exact surgical two-year anniversary or exact five-year anniversary. In the decompression alone group, since there is no device, this endpoint will be identified as any serious AE that is classified as definitely related to surgery.

**Note:** The IDE study defined this CCS component as severe and definitely-related and not as serious and definitely-related. This has been changed to serious and definitely related for consistency with other spine studies for Objectives 2 and 3 only.

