### **3.2. Primary Endpoints**

The identical Month 24 CCS endpoint as was used in the IDE will be used to compare PAS results to IDE study results, and to update the Bayesian posterior probabilities of non-inferiority and superiority relative to fusion. This CCS definition requires no Treatment Failure (i.e., no reoperation, revision, replacement, or supplemental fixation at the index level(s) and no epidural injection at any lumbar level); an ODI improvement  $\geq 15$ ; as well as no new or worsening, persistent neurological deficit; and no major device-related adverse event defined as severe and definitely-related

The CCS endpoints using in Objective 2 and 3 replace severe device-related AEs with serious device-related AEs for greater consistency with other spine studies. The relationship will be evaluated relative to the device and the surgical procedure since controls receive no device. For comparison to decompression alone, any surgical intervention at the index site will imply clinical failure.

Month 60 success for this comparison will require the following items:

- At least a 15 point improvement relative to pretreatment baseline in the Oswestry Disability Index (ODI, range 0-100).
- No reoperations, revisions, removals, or supplemental fixation at the index level(s);
- No  $\geq 2$  injections or series of injections for any lumbar level\*\*, or nerve block procedures performed to treat spinal stenosis at any lumbar level(s); or a single injection within 12 months of the 5 year endpoint.

\*\*A series of injections is considered 2-3 injections performed between 24-hour and one week intervals designed to treat a single pain event. Secondary injections performed due to patient demand or recurrence of symptoms following the initial injection are considered separate injections and would constitute a study failure.

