## 5. Performance Evaluation and Measurements

### 5.1. Primary Variables of Performance

Month 60 composite success will require the following items (Objective 1):

- At least a 15 point improvement relative to pretreatment baseline in the Oswestry Disability Index (ODI, range 0-100).
- No reoperations, revisions, removals, or supplemental fixation at the index level(s);
- No  $\geq 2$  injections or series of injections for any lumbar level\*\*, or nerve block procedures performed to treat spinal stenosis at any lumbar level(s); or a single injection within 12 months of the 5 year endpoint.

\*\*A series of injections is considered 2-3 injections performed between 24-hour and one week intervals designed to treat a single pain event. Secondary injections performed due to patient demand or recurrence of symptoms following the initial injection are considered separate injections and would constitute a study failure.

For Objectives 2 and 3, the Month 24 CCS from the IDE will be slightly modified to include any surgical intervention at index level(s). This is because the decompression only group receives no device. In summary, when comparing coflex® in conjunction with decompression to decompression alone, Month 24 CCS will require.

- No “Treatment Failure” on or before the exact 2-year anniversary of the index surgery).
- At least a 15 point improvement relative to pretreatment baseline in the Oswestry Disability Index (ODI, range 0-100).
- No persistent new or worsening sensory or motor deficit where persistence is established by identifying new or worsening deficits at Month 12 that do not resolve by Month 24.
- No major device-related adverse event defined as an event simultaneously both ‘Serious’ and ‘Definitely’ related to the implant on or before the exact surgical two-year anniversary.

Treatment Failure will include:

- No surgical intervention at the index level
- No lumbar epidural steroid injection including nerve root blocks and facet blocks at any lumbar level.

The identical Month 24 CCS endpoint used in the IDE study will be used to compare PAS results to IDE study results and to update the Bayesian posterior probabilities of non-inferiority and superiority relative to fusion (Objective 4).

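### In the Month 24 CCS for Objectives 2 and 3, controls fail for serious surgery-related events but coflex patients only for serious device-related events; one rule is needed for both arms.

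*Combined protocol and SAP*

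**What the plan says.** Section 6.4.1 defines the item separately for each cohort. A coflex patient fails for an event "simultaneously having a severity rating of 'Serious' and a device relatedness of 'Definitely". For controls, "this endpoint will be identified as any serious AE that is classified as definitely related to surgery".

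The definition of the Objective 2 and 3 endpoint repeats the split. The synopsis requires "No major device-related adverse event defined as an event simultaneously both" serious and definite, and then adds for the decompression group that "since there is no device, this endpoint will be identified as any serious AE that is classified as definitely related to surgery". Section 3.1, Objective 2, does the same: "In the decompression alone group, since there is no device, this endpoint will be identified as any serious AE". The narcotics-modified Month 24 CCS (synopsis, 3.3 and 5.2) carries the same control sentence.

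Two other sections do not match:

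- Section 5.1 counts only events "related to the implant on or before the exact surgical two-year anniversary" and has no sentence for controls.
- Section 3.2 says "The relationship will be evaluated relative to the device and the surgical procedure since controls receive no device". It does not say whether both relationships apply in both arms or one applies in each.

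The time window also varies. The synopsis definition for Objectives 2 and 3 and section 5.1 stop at two years. Section 3.1 and the modified CCS use "on or before the exact surgical two-year anniversary or exact five-year anniversary", although the item belongs to a Month 24 endpoint.

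**The concern.** The absence of a device explains why device relatedness cannot be used in controls. It does not explain why procedure relatedness is not counted in coflex patients, who have the same decompression.

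The item feeds the comparison against the -0.10 margin (Objective 2) and the superiority test (Objective 3). It also carries over to the treadmill version of the CCS in section 7.8, which replaces only the ODI component. Objective 1 has no adverse-event item and Objective 4 uses the IDE definition, so neither is affected.

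Nothing later in the plan removes the difference. Propensity score subclassification balances baseline covariates. Review by the Clinical Events Committee (CEC, section 7.19) can reclassify an event but does not change which class of event counts in which arm.

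**Working it through.** **Direction.** Take an otherwise successful patient with a serious event that is definitely related to surgery and not to the device.

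| Rule | Coflex | Control |
|---|---|---|
| Written (6.4.1, synopsis, 3.1) | success | failure |
| Device or procedure, both arms | failure | failure |
| Device only, both arms | success | success |

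Against the second row the written rule removes coflex failures; against the third it adds control failures. Both favour coflex. Against a surgery-only rule in both arms the direction is not determined. Section 5.1 read alone works the other way, since controls could not fail the item at all.

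**Who is affected.** Index-level surgery, lumbar injection and insufficient ODI improvement already fail patients in both arms, and section 6.3 requires no alternative cause for a Definite rating. What remains is, for example, a dural violation without re-operation or a pulmonary embolism that prolongs hospitalization (events listed in 6.1; seriousness in 6.4).

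**Size without an event rate.** With 150 per arm, one control failed by this item whose coflex counterpart passes shifts the observed difference by 1/150 = 0.67 percentage points.

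**Illustration.** Let x be the share of otherwise successful patients in each arm with such an event. This is an assumption; the documents give no rate. At success 0.662 the apparent gain for coflex is 0.662x: 0.7, 1.3 and 3.3 points at x = 1, 2 and 5%, or about 1, 2 and 5 controls of 150.

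Inputs from 7.4, 7.5, 7.7.2 and 7.7.3: 150 per arm, coflex prior beta(135.5, 69.5), control prior beta(0.5, 0.5), threshold 0.95, margin -0.10 for Objective 2 and 0 for Objective 3, coflex success 0.662.

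With y successes per arm, the claim is made when P(π_coflex − π_control > margin) ≥ 0.95, where π_coflex ~ beta(135.5 + y, 69.5 + 150 − y) and π_control ~ beta(0.5 + y, 0.5 + 150 − y), each with its own y. Summing binomial probabilities over all 151 × 151 outcomes gives the exact rate of claims.

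*The plan's own figures first.* At x = 0, power is 0.864 for Objective 2 (stated 89%) and 0.861 for Objective 3 at 12.5 points (stated 88%). Objective 2 type 1 error is 0.033 with the prior and 0.052 without (stated 0.052 and 0.042). The stated figures are not reproduced: the simulation memo is not available and subclass averaging is not modelled. Only differences between rules should be read from what follows.

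*True rates used for false claims.*

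- Objective 3, written: coflex 0.662, control 0.662(1−x). Common: both 0.662(1−x).
- Objective 2, written: coflex 0.662, control 0.662(1−x) + 0.10. Common: coflex 0.662(1−x), control 0.662(1−x) + 0.10.

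Probability of a false claim, written rule / common device-or-procedure rule:

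| x | Obj. 3, stated prior | Obj. 2, stated prior | Obj. 3, non-informative | Obj. 2, non-informative |
|---|---|---|---|---|
| 0 | 0.035 / 0.035 | 0.033 / 0.033 | 0.050 / 0.050 | 0.052 / 0.052 |
| 1% | 0.050 / 0.043 | 0.048 / 0.041 | 0.064 / 0.051 | 0.067 / 0.052 |
| 2% | 0.068 / 0.052 | 0.067 / 0.050 | 0.081 / 0.051 | 0.085 / 0.052 |
| 5% | 0.154 / 0.088 | 0.162 / 0.089 | 0.151 / 0.052 | 0.157 / 0.051 |

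At x = 0.5% with the stated prior, the written rule adds 0.003 in each objective. The rise that remains under the common rule with the stated prior comes from the prior, which is still centred on the IDE's device-related item. With a rescored prior (135(1−x) successes of 204) the error stays at about 0.035 (Objective 3) and 0.033 (Objective 2) at every x.

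**The case against.** The strongest objection is that section 3.2, which addresses Objectives 2 and 3 directly, can be read as applying both relationships to both arms. The design would then be close to symmetric and the defect would be one of drafting. That reading is possible, but it contradicts the explicit split in 6.4.1, the synopsis and 3.1. The other reading, one relationship per arm, repeats the split. Reconciliation is needed either way.

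It can also be said that 5.1 borrows a term which 6.4.1 defines for controls. That is a fair way to fill the gap, but it leads back to the asymmetric rule.

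The affected group may be smaller than the examples suggest. Section 5.1 also fails either arm for a persistent new or worsening deficit (the synopsis and 3.1 definitions omit this), and sections 4.12 and 7.2 count intraoperative failures as CCS failures. Both routes narrow the group; neither reverses the direction.

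The numbers rest wholly on an assumed x. With the stated prior, the rule's own contribution to Objective 3 error is only 0.007 at 1% and 0.016 at 2%, and part of the 0.154 at 5% is prior mismatch. For Objective 2 the size also depends on how the null is set: applying x to 0.762 gives 0.074 instead of 0.067 at 2%, and 0.195 instead of 0.162 at 5%. All of this stands, and it limits the figures to illustration.

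The five-year wording is a separate drafting point. It is included because it sits in the same item and needs the same edit.

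**Conclusion.** The concern holds. As written in 6.4.1, the synopsis and 3.1, the major adverse event item treats the same surgical event as failure in controls and not in coflex patients. Relative to either common rule in the table of rules, the effect can only favour coflex in Objectives 2 and 3. The stated reason does not justify it, and 3.2 and 5.1 do not resolve it.

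The size is not known and may be near zero. It depends on how often a serious, definitely surgery-related, non-device event occurs in a patient who otherwise succeeds. The calculations assume an equal rate x in both arms, 150 evaluable patients per arm and no subclass averaging; no break-even rate is claimed. This should be corrected before outcomes are unblinded. Confidence is medium, because the direction is clear and the magnitude is not.

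**What to change.** Define the item identically in both arms: failure if the patient has an adverse event that is serious (section 6.4) and definitely related to the device or the index surgical procedure, by CEC classification, on or before the two-year anniversary.

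- Use this wording wherever the Objective 2/3 CCS or the modified Month 24 CCS is defined: synopsis, 3.1, 3.2, 3.3, 5.1, the modified CCS in 5.2, and 6.4.1. Remove the five-year alternative from these Month 24 items.
- Leave unchanged the separate implant-related secondary endpoint at two and five years in 5.2, and the IDE definition for Objective 4.
- Report the written arm-specific rule and a device-only rule as sensitivity analyses.
- If the IDE data record procedure relatedness, rescore the coflex prior for Objectives 2 and 3. If they do not, keep the stated prior, disclose the mismatch in definitions, and add a non-informative-prior run as a sensitivity analysis.

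**Cost.** No new data collection: section 6.4 already has relationship to device and to procedure on the adverse event form. Coflex success becomes slightly lower. With the common rule and a rescored prior, power at x = 0, 1, 2 and 5% is 0.86, 0.85, 0.84 and 0.82 for Objective 3 (coflex 0.662(1−x), control 0.537(1−x)) and 0.86, 0.86, 0.86 and 0.84 for Objective 2 (control 0.642(1−x)).

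The fallback is only a partial repair: with the stated prior kept, Objective 3 error under the common rule is still 0.052 at 2% and 0.088 at 5%. The non-informative run has much lower power at x = 0 (0.720 against 0.861 for Objective 3, 0.709 against 0.864 for Objective 2), so it should remain a sensitivity analysis. The IDE data would need re-tabulation if procedure relatedness was recorded, which the documents do not say, and the Objective 2 and 3 operating characteristics would need to be re-run.
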